2.4.5.2 Analyses of laboratory variables

Clinical laboratory values are expressed in Standard International (SI) units. Laboratory data collected and recorded as below the limit of detection are set equal to the lower limit of detection for the calculation of summary statistics.

Summary data for each laboratory parameter are presented for each continuous clinical laboratory parameter (including hematology, serum chemistry, coagulation studies and liver function tests). Descriptive statistics are presented for the actual values, change from baseline, and percent change from baseline by visit and observation period.

For each continuous laboratory parameter, results are categorized as low, normal, or high based on the laboratory normal ranges.

A listing is produced for all patients with abnormal liver function tests defined as an ALT $>3 \times$ ULN, AST $>3 \times$ ULN, and/or total bilirubin $>2 \times$ ULN at any time point.

A table is produced to summarize the number and percentage of patients in each of below categories at any post-baseline time point by observation period.

- ALT >1 & ≤ 3 , >3 & ≤ 5 , >5 & ≤ 10 , >10 & ≤ 20 , $>20 \times$ ULN,
- AST >1 & ≤ 3 , >3 & ≤ 5 , >5 & ≤ 10 , >10 & ≤ 20 , $>20 \times$ ULN,
- ALT or AST >1 & ≤ 3 , >3 & ≤ 5 , >5 & ≤ 10 , >10 & ≤ 20 , $>20 \times$ ULN,
- ALP $>1.5 \times$ ULN,
- Total Bilirubin >1.5 & ≤ 2 , >2 & ≤ 3 , >3 & ≤ 5 and $>5 \times$ ULN,
- Total Bilirubin $>2 \times$ ULN concurrent with ALT or AST $>3 \times$ ULN,
- INR >1.2 .

In separate figures, the peak total bilirubin (at any time post-baseline) is plotted against the peak AST, the peak ALT, and the peak AST or ALT levels at any time post-baseline by observation period. The mean of ALT, AST, and total bilirubin will be plotted over time. The Kaplan-Meier curve for the time to first onset of ALT >3 ULN, AST >3 ULN and AST/ALT >3 ULN will be provided.

For hematology and blood chemistry, summary tables of potentially clinically significant abnormalities (PCSA) are provided by observation period.

Laboratory data will be provided in data listings as appropriate. Values that meet a PCSA criterion or out-of-range laboratory values when no PCSA criterion is defined will be identified in the listings.

2.4.5.3 Analyses of physical examination and vital sign variables

The summary statistics (including number, mean, median, Q1, Q3, standard deviation, minimum and maximum) of all vital sign variables are calculated for each visit or study assessment in factor or BPA prophylaxis period and fitusiran prophylaxis period. Summary table of potentially clinically significant abnormalities (PCSA) are provided by observation period.

Vital sign measurements are presented for each patient in a data listing as appropriate, with abnormal vital signs flagged.

All physical examination findings are presented in a by-patient data listing.

2.4.5.4 Analyses of electrocardiogram variables

PR, QRS, QT, QTc and RR intervals and their change from baseline values are summarized by scheduled visit for each observation period. Besides, their change from time-matched and pre-dose baseline are also summarized in fitusiran prophylaxis period by scheduled visit. Participants are categorized into ≤ 450 , $>450 - 480$, $>480 - 500$, or >500 ms per their maximum post-baseline absolute QTc interval and ≤ 30 , $>30 - 60$, or >60 ms per their maximum change from baseline QTc interval. The number and percentage of participants in each category are summarized.

For post-baseline assessments where ECG is performed in triplicate, the average of the 3 (or all available) readings is used for analysis.

2.4.6 Analyses of pharmacokinetic and pharmacodynamic variables

2.4.6.1 Analyses of pharmacodynamic variables

2.4.6.1.1 Antithrombin

AT levels and AT lowering (% lowering from baseline) in the fitusiran prophylaxis period are summarized descriptively.

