6.5 MONITORING AND MANAGEMENT OF THROMBOTIC EVENTS

As serious vascular (arterial and venous) thrombotic events have been reported in patients exposed to fitusiran, Investigators should have a low threshold to evaluate signs and symptoms potentially consistent with these diagnoses. Signs and symptoms of vascular thrombotic events may include, but are not limited to, severe or persistent headache, headache with nausea and vomiting, chest pain and/or tightness, coughing up blood, trouble breathing, abdominal pain, fainting or loss of consciousness, swelling or pain in the arms or legs, vision problems, weakness and/or sensory deficits, and changes in speech.

An evaluation of signs and symptoms potentially consistent with vascular thrombosis should include appropriate imaging studies as applicable. For the diagnosis of cerebral venous sinus thrombosis magnetic resonance imaging venogram (MRV) or computed tomography venogram (CTV) is recommended ([15](#)).

If a patient develops thrombosis while on fitusiran, AT reversal is recommended in combination with factor or BPA replacement and appropriate anticoagulation. AT reversal should follow labeled product recommendations for the prevention of perioperative thrombosis in patients with AT deficiency, and individualize patient doses to target 80-120% AT activity. The use of plasma derived AT may be preferable to recombinant AT, given its longer half-life. It is recommended that cases of thrombosis are discussed with the study Medical Monitor and Clinical Advisor (see [Section 7.6.6.1](#) for further information regarding Adverse Events of Special Interest). For the United States specific requirements, see [Section 11.6.1.2](#). For the Japan specific requirements, see [Section 11.6.2](#).

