The factor/BPA prophylaxis period, fitusiran onset period, efficacy period and treatment period also exclude the period of following intercurrent events to avoid confounding of treatment effect for the primary efficacy analysis based on On-Treatment Strategy.

- Permanent fitusiran treatment discontinuation during treatment period: Exclude events occurring on any dates starting from the date of the last dose within treatment period +29 days. For patients whose last dose is on 50 mg/20 mg Q2M regimen, the “29 days” adjustment will be replaced with 57 days.
- Perioperative period of major surgery. The perioperative period is defined as the day of the surgery through the final day on which supplemental hemostatic or antithrombotic treatments are administered as part of the perioperative treatment plan.
- Period of minor surgery is defined as the perioperative period of surgery above or to 72 hours from the end of surgery, whichever is later.
- Period of antithrombin treatment is defined as the first day of antithrombin treatment through the final day on which antithrombin or other anticoagulant therapies are administered plus 5 half-lives of that specific product.
- After prophylactic treatment with emicizumab.

The summary statistics for number of patients who are lost-to-follow-up and who had each intercurrent event will be provided.

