2.1.4 Safety endpoints

The safety analysis will be based on the reported adverse events (AEs) including SAEs and other safety information, such as clinical laboratory data, vital signs, weight and height, physical examination, ECG findings, and ADA detection/assessment.

Observation period:

- Factor/BPA prophylaxis period is defined as the time from enrollment (Month-6 visit) up to the 1st dose of fitusiran.
- Fitusiran prophylaxis period is defined as the time after the 1st dose of fitusiran up to the end of the study (defined as last protocol planned visit). It includes the following 2 periods:
 - Fitusiran treatment period is defined as the time after the 1st dose of fitusiran to the EOS/ET visit,
 - Follow up period is defined as the time after Fitusiran treatment period up to the end of the study.

The treatment-emergent adverse event period equals fitusiran prophylaxis period.

On-study observation period includes both factor/BPA prophylaxis period and fitusiran prophylaxis period.

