2.4.6.1.2 Peak thrombin

Peak thrombin values collected within 48 hours of factor, BPA or antifibrinolytic administration are excluded from all analysis. Peak thrombin values in the fitusiran prophylaxis period are summarized descriptively.

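### The SAP has no rule for AT activity values measured during or shortly after AT concentrate, so any such value would count as lack of AT lowering

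*SAP*

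**What the plan says.** **AT activity.** SAP 2.4.6.1.1 reads in full: "AT levels and AT lowering (% lowering from baseline) in the fitusiran prophylaxis period are summarized descriptively". SAP 2.4.7.8 (AT activity over time) only refers back to it. The period is long: "Fitusiran prophylaxis period is defined as the time after the 1st dose of fitusiran up to the end of the study" (SAP 2.1.4), which takes in follow-up. Protocol 8.2.6 adds that the summary is by scheduled visit. SAP 2.4.6.1.3 pairs AT and thrombin by sampling day. Nothing in these sections or in SAP 2.5 mentions AT concentrate.

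**Peak thrombin.** The next subsection, SAP 2.4.6.1.2, does have a rule: "Peak thrombin values collected within 48 hours of factor, BPA or antifibrinolytic administration are excluded from all analysis". It does not name AT concentrate.

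**Bleeding rate.** Among the intercurrent events removed from the on-treatment analysis, SAP 2.1.3.1 has a window that opens when AT treatment starts. Its end is tied to the last day when "antithrombin or other anticoagulant therapies are administered plus 5 half-lives of that specific product".

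**Use of AT concentrate.** Protocol 6.5 says: "If a patient develops thrombosis while on fitusiran, AT reversal is recommended", and that sites should "individualize patient doses to target 80-120% AT activity". Protocol 6.3.2.2 with Table 6, 6.3.2.3 and 6.6 also raise AT replacement for larger or repeated factor or bypassing-agent doses, after discontinuation, and in surgery.

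**The concern.** Two parts of the SAP accept that outside treatment can mask what fitusiran is doing: one for peak thrombin, one for the bleeding rate. AT activity is the variable that AT concentrate changes directly, and it has neither protection. A sample at 80-120% activity after replacement would be tabulated as little or no lowering by fitusiran, when it reflects infused antithrombin.

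Affected samples are possible under the plan. AT is scheduled every half month for the first two months of fitusiran and monthly after that (SAP 2.1.6). Patients who stop the drug are encouraged to stay for the remaining assessments (Protocol 5.3.1). Unscheduled pharmacodynamic values can fill a visit window that has no scheduled value (SAP 2.5.4).

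At stake are the mean and SD of AT lowering at the affected visits, any mixed model fitted to AT (Protocol 8.2.6 allows one, and SAP Appendix A lists one for pharmacodynamic variables), and the AT-thrombin correlation, where a replaced value would lie far from the other pairs.

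**Working it through.** The plan states no figure that depends on this rule, so there is nothing to reproduce. The size has to be illustrated.

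**Inputs**
- True mean lowering: 85.9%, the mean maximal reduction at 80 mg in the extension study (Protocol 1.2.2.3). It stands in for a visit mean.
- AT activity after replacement: 80, 100 or 120% (range in Protocol 6.5).
- Baseline AT activity: 100% (assumed). Apparent lowering after replacement, L, is then +20, 0 or -20%.
- n at a visit: 30 (planned Cohort A), 50 (planned Cohort B), 80 (planned total).
- k, the number of affected patients at that visit: not in the documents, so varied from 0 to 3.

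**Formula**

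Observed mean lowering = [(n - k) × 85.9 + k × L] / n, so the shortfall is k × (85.9 - L) / n. The three values of 85.9 - L are 65.9, 85.9 and 105.9.

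| n | k | Shortfall in points (L = +20, 0, -20) | Observed mean lowering, % |
|---|---|---|---|
| any | 0 | 0 | 85.9 |
| 80 | 1 | 0.8, 1.1, 1.3 | 85.1, 84.8, 84.6 |
| 80 | 3 | 2.5, 3.2, 4.0 | 83.4, 82.7, 81.9 |
| 50 | 1 | 1.3, 1.7, 2.1 | 84.6, 84.2, 83.8 |
| 30 | 1 | 2.2, 2.9, 3.5 | 83.7, 83.0, 82.4 |
| 30 | 3 | 6.6, 8.6, 10.6 | 79.3, 77.3, 75.3 |

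Example: n=30, k=1, L=0 gives (29 × 85.9 + 0) / 30 = 83.0, a shortfall of 2.9.

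**Sensitivity to baseline.** With a baseline of 80%, activity of 80-120% reads as a lowering of 0 to -50%. One affected patient at n=30 then costs (85.9 - 0)/30 = 2.9 to (85.9 + 50)/30 = 4.5 points.

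**Median and SD.** A simulation used n=80 and residual AT drawn from a lognormal distribution with median 13.5% and log-scale SD 0.32 (both assumed). One value was set to zero lowering, averaged over 4,000 runs:

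| | No affected patient | One affected patient |
|---|---|---|
| Mean lowering, % | 85.8 | 84.7 |
| Median lowering, % | 86.5 | 86.4 |
| SD | 4.6 | 10.7 |

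The SD more than doubles while the median moves by about 0.1 point.

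These shifts apply to a sample taken near the target range. A sample late in the washout, with less concentrate left, would cost less.

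**The case against.** The strongest case against is that the problem may never arise. It needs a patient who received AT concentrate and a recorded AT value inside the washout. The documents give no count of such patients and no AT half-life. The exposure is also narrower than the wording of 2.4.6.1.1 suggests:
- Scheduled values take precedence and only one value per window is used (SAP 2.5.4).
- AT samples tied to bleeds and surgery are mostly drawn before treatment (Protocol Tables 2 and 12).
- Tests that guide care may be local (Protocol 7.3) and may not reach the central data.
- For the correlation, thrombin values within 48 hours of factor or bypassing agent already drop out.

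All of this stands. It limits the size but does not supply the missing rule.

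A reader might infer more than the documents support:
- **That AT lowering is in fact understated.** This cannot be said; the effect is conditional.
- **That dose selection or the AT safety threshold rests on this summary.** Dose selection used Phase 1 and 1/2 data and modelling (Protocol 1.4). The rule at AT below 15% acts on individual results during the study (Protocol 6.2.3.2). AT activity over time is an exploratory endpoint.
- **That the low tail is hidden.** SAP 2.5.1 requires the median, quartiles, minimum and maximum. Other patients' low values stay visible, and a replaced value would tend to show at the maximum of activity. Excluding it brings back no low value.
- **That AT-treated patients are those with the lowest AT.** The stated triggers are thrombosis, factor or bypassing-agent dosing needs, and surgery. None is defined by an AT level.
- **That the 2.1.3.1 window can be reused unchanged.** It also runs through other anticoagulants. Protocol 6.5 pairs AT reversal with anticoagulation, so that window could discard valid AT values after the concentrate has cleared.

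**Conclusion.** The gap is real and minor. Followed as written, the plan would count infused antithrombin as absence of a fitusiran effect, which conflicts with how it treats peak thrombin and the on-treatment bleeding rate.

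On the assumptions shown, one affected patient lowers the visit mean by about 1 point in the pooled set and by 2.2 to 3.5 points in Cohort A, which is analyzed separately. It also inflates the SD and leaves the median almost unchanged. The direction is firm for samples near the replacement target. The size depends on how many patients are affected and when they are sampled, neither of which is in the documents. With none affected there is no bias. The bleeding endpoints are untouched.

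**What to change.** In SAP 2.4.6.1.1 and 2.4.6.1.3, add a rule that AT activity values are excluded from the first AT-product administration to the last AT-product administration plus 5 half-lives of that product. State that the window is not extended for other anticoagulants, unlike the one in 2.1.3.1. List the excluded values by patient, and show the all-values summary as supportive.

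The cost is about one sentence in each section, one derived flag and one listing. The AT-treatment dates and product half-lives are already needed for 2.1.3.1, so no new data are required. The rule should be set before database lock so that it is not a post-hoc choice. The downside is fewer AT values at later visits for AT-treated patients. If those patients differ in AT level from the rest, that missingness is informative, and the supportive all-values summary lets a reader see its effect.

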2.4.6.1.2 Peak thrombin

Peak thrombin values collected within 48 hours of factor, BPA or antifibrinolytic administration are excluded from all analysis. Peak thrombin values in the fitusiran prophylaxis period are summarized descriptively.

2.4.6.1.3 AT lowering and peak thrombin

Correlation between AT (actual AT levels and AT lowering) and thrombin is computed on paired assessments, where both parameters are measured on the same day. Log transformation may be used.

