| | | Month -6 | Month -5 | Month -4 | Month -3 | Month -2 | Month -1 | Onset period ^b | | Efficacy period | | | | | | | | |
| | | | | | | | | Baseline | Month 1 | Month 2 | Month 3 | Month 4 | Month 5 | EOT | EOS/ET ^{c,d} | Month 8 | | |
| Study day (±Visit Window) | -228 to -169 | Day -168 | Day -140 ±7 | Day -112 ±7 | Day -84 ±7 | Day -56 ±7 | Day -28 ±7 | Day 1 | Day 15 ±3 | Day 29 ±7 | Day 43 ±3 | Day 57 ±7 | Day 85 ±7 | Day 113 ±7 | Day 141 ±7 | Day 169 ±7 | Day 197 ±7 | Day 225 ±7 |
| Informed Consent/Assent | X | | | | | | | | | | | | | | | | | |
| Medical History ^f | X | | | | | | | | | | | | | | | | | |
| Demographics | X | | | | | | | | | | | | | | | | | |
| Inclusion/Exclusion Criteria | X | | | | | | | | | | | | | | | | | |
| Enrollment | | X | | | | | | | | | | | | | | | | |
| eDiary Training ^g | X | | | | | | | | | | | | | | | | | |
| Physical Examination ^h | X | X | X | X | X | X | X | X | X | X | X | X | X | X | X | X | X | X |
| Body Weight and Height ⁱ | X | X | X | X | X | X | X | X | X | X | X | X | X | X | X | X | X | X |
| Vital Signs | X | X | X | X | X | X | X | X | X | X | X | X | X | X | X | X | X | X |
| 12-Lead ECG ^j | X | X | | | | | | X | | | | | | | | | X | |
| FibroScan OR FibroTest/APRI ^k | X | | | | | | | | | | | | | | | | | |
| TG Level ^l | X | | | | | | | X | X | X | X | X | X | X | X | X | X | X |

Table 1 - Schedule of assessments

| Study visit (Month) | Screening | Factor or BPA prophylaxis period ^a | | | | | | Fitusiran treatment period ^b | | | | | | | | | | AT F/U ^{d,e} | |
|---|--------------|---|-------------|-------------|------------|------------|------------|---|-----------|-----------------|-----------|-----------|-----------|------------|------------|-----------------------|------------|-----------------------|--|
| | | Month -6 | Month -5 | Month -4 | Month -3 | Month -2 | Month -1 | Onset period ^b | | Efficacy period | | | | | | | | | |
| | | | | | | | | Baseline | Month 1 | Month 2 | Month 3 | Month 4 | Month 5 | EOT | | EOS/ET ^{c,d} | | | |
| Study day (±Visit Window) | -228 to -169 | Day -168 | Day -140 ±7 | Day -112 ±7 | Day -84 ±7 | Day -56 ±7 | Day -28 ±7 | Day 1 | Day 15 ±3 | Day 29 ±7 | Day 43 ±3 | Day 57 ±7 | Day 85 ±7 | Day 113 ±7 | Day 141 ±7 | Day 169 ±7 | Day 197 ±7 | Day 225 ±7 | |
| Coagulation and TG Level Pre/Post Factor or BPA Administration ^l | | X Performed at any one visit ^m | | | | | | | | | | | | | | | | | |

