8.2.6 Pharmacodynamic analysis

AT and thrombin levels will be summarized descriptively by scheduled visit. Mixed models repeated measures analyses may be performed as deemed appropriate. Correlation between AT and thrombin levels may be explored.

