Approximately 80 patients are planned for enrollment in this study, including approximately 30 patients with inhibitors (Cohort A) and approximately 50 patients without inhibitors (Cohort B). Approximately 18 patients with hemophilia B (including approximately 7 hemophilia B patients in Cohort A, among which are a subgroup of no more than 4 patients who are not responding adequately to BPA prophylaxis), and approximately 7 adolescents (≥ 12 to < 18 years of age) are also planned for enrollment. In the US, only patients from Cohort A are included.

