2.1.6 Pharmacodynamic endpoints

In this study AT activity level and thrombin generation (TG) over time are collected as measurements of PD effect and coagulation assessments are collected for exploratory analyses of PD effect.

AT activity level and TG are assessed at screening, Day 1 and then every half month in the first two months of fitusiran treatment period and then every month in the remaining study period.

During the factor/BPA prophylaxis period (before fitusiran treatment), patients undergo a coagulation and peak thrombin/thrombin generation response assessment with timed blood collections both before and following a dose of their routine factor/BPA prophylaxis doses.

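### The AT–peak thrombin correlation is defined on same-day pairs, about nine per patient, with no rule for the repeated pairs; a single coefficient would blend within- and between-patient association

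*SAP*

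**What the plan says.** SAP 2.4.6.1.3 correlates AT, both as actual level and as lowering, with thrombin. The calculation "and thrombin is computed on paired assessments, where both parameters are measured on the same day", and "Log transformation may be used". The section names no coefficient, no set of visits, no rule for several pairs from one patient, and no interval or test.

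The two markers share a schedule. SAP 2.1.6 has it that "AT activity level and TG are assessed at screening, Day 1 and then every half month in the first two months" of fitusiran treatment and "then every month in the remaining study period". SAP 2.4.6.1.2 adds one exclusion: "Peak thrombin values collected within 48 hours of factor, BPA or antifibrinolytic administration are excluded from all analysis".

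Protocol 8.2.6 is more tentative: "Correlation between AT and thrombin levels may be explored". It also allows mixed models for the pharmacodynamic (PD) data. The PD-variables row of SAP Appendix A lists descriptive statistics and a mixed model for repeated measures, without mentioning the correlation.

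Elsewhere the SAP states how it handles dependence within a participant. A robust sandwich covariance is specified for the bleed model (2.4.4.1.1), the Cox model (2.4.4.1.3) and the Haem-A-QOL model (2.4.4.2.4).

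**The concern.** The unit of the calculation is the assessment pair, and each patient supplies many pairs. The plain reading is therefore one coefficient over clustered data. Two different questions are then answered by one number:

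- Does thrombin rise when a given patient's AT falls?
- Do patients with lower average AT have higher average thrombin?

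A reader of the report could not tell which of the two the coefficient reflects. If someone attached a confidence interval or p-value based on the number of pairs, it would claim more precision than the number of patients supports.

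**Working it through.** **Inputs from the documents**

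- Visits: Table 1 of the protocol schedules AT and thrombin generation together on Days 15, 29, 43, 57 and 85, then "Day 113 ±7 | Day 141 ±7 | Day 169 ±7 | Day 197 ±7". That is 9 post-baseline pairs per patient, 10 with Day 1 and 11 with screening as well. Patients who do not enter the extension add follow-up pairs. The 48-hour exclusion removes some.
- Patients: "Approximately 80 patients are planned for enrollment in this study", about 30 in Cohort A and 50 in Cohort B. Pairs are therefore at most 80 × 9 = 720 (30 × 9 = 270 and 50 × 9 = 450 by cohort).
- The plan gives no correlation, standard deviation or ICC for this analysis, so there is no planned figure to reproduce.

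**Assumptions (not in the documents).** The within-patient correlation r_w, the between-patient correlation r_b, and the ICCs of AT and peak thrombin. A range is shown for each.

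**Step 1: what one coefficient over all pairs estimates**

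r_pooled = r_b·√(ICC_AT·ICC_T) + r_w·√((1 − ICC_AT)(1 − ICC_T))

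| r_w | r_b | ICC_AT / ICC_T | Calculation | r_pooled |
|---|---|---|---|---|
| −0.60 | 0 | 0.05 / 0.05 | −0.60 × 0.95 | −0.57 |
| −0.60 | 0 | 0.3 / 0.3 | −0.60 × 0.7 | −0.42 |
| −0.60 | 0 | 0.05 / 0.5 | −0.60 × √(0.95 × 0.5) | −0.41 |
| −0.60 | 0 | 0.5 / 0.5 | −0.60 × 0.5 | −0.30 |
| −0.80 | −0.80 | 0.5 / 0.5 | −0.40 − 0.40 | −0.80 |
| −0.80 | −0.80 | 0.2 / 0.8 | −0.32 − 0.32 | −0.64 |
| −0.20 | −0.80 | 0.5 / 0.5 | −0.40 − 0.10 | −0.50 |
| −0.20 | −0.80 | 0.8 / 0.8 | −0.64 − 0.04 | −0.68 |

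Rows 1 to 4 understate the within-patient value, row 5 matches it, and the last two rows overstate it. Row 6 is weaker than both components even though they agree.

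**Step 2: check by simulation** (80 patients, nine pairs each, 1,500 runs). With r_w = −0.20, r_b = −0.80 and both ICCs 0.8, the pooled coefficient averages −0.68, the patient-centred one −0.20 and the correlation of patient means −0.78. With r_w = −0.80, r_b = 0 and ICCs of 0.5 (AT) and 0.8 (thrombin), the three are −0.25, −0.80 and −0.04. Separate estimates recover the within-patient value exactly and the between-patient value closely.

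**Step 3: precision, only if an interval or test were added.** Under no association the variance of the pooled coefficient is inflated by about 1 + (9 − 1)·ICC_AT·ICC_T.

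- ICCs 0.5: 1 + 8 × 0.25 = 3.0, so the standard error is √3 = 1.73 times the naive one. A nominal 5% test rejects when |z| > 1.96/1.73 = 1.13, about 26% of the time. Simulation gives 25% to 27% for 30, 50 and 80 patients.
- ICCs 0.8: 1 + 8 × 0.64 = 6.12, standard-error ratio 2.47, about 43%. Simulation gives 42% to 45%.
- ICCs 0.3: 1 + 8 × 0.09 = 1.72, ratio 1.31, about 14%.
- ICCs 0.05: 1 + 8 × 0.0025 = 1.02, about 5%, so no practical inflation.

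**Step 4: why the visit set matters.** Entry requires AT of at least 60% (Protocol 5.2, E 03), while residual AT in earlier monthly-dose data was about 10% to 20% (Protocol 1.4). Day 1 pairs therefore sit far from the on-treatment pairs, and including or omitting them could move the coefficient substantially. The SAP does not say which applies.

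**The case against.** The other side has several good points.

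- **The text does not say that pairs are pooled or independent.** It can be read as a matching rule only. Protocol 8.2.6 summarizes AT and thrombin by visit, and a separate correlation at each visit, with one pair per patient, would fit. This stands: a reader might infer a declared independence assumption, and there is none. But nothing in SAP 2.4.6.1.3 points to by-visit coefficients, and the single-coefficient reading is the plain one.
- **No interval or test is planned here.** This stands. The error rates in step 3 are conditional and are not a forecast of the report.
- **A claim that the pharmacodynamic link will be badly understated does not follow.** It requires between-patient correlation near zero. Step 1 shows agreement or overstatement under other values, and the documents favour none.
- **Some between-patient sources are already limited.** All patients have severe disease, the cohorts are analysed separately before pooling, both assays are read centrally, and AT lowering is relative to the patient's own baseline. This reduces the mixing but does not remove it; thrombin is not baseline-adjusted.
- **The between-patient contrast is informative.** Protocol Table 3, for simulated 50 mg monthly dosing, gives a median trough of 17.2 and median peak of 18.23, against a 5th to 95th percentile trough range of 10.3 to 29.6. Much of the steady-state AT spread may lie between patients, so a purely within-patient coefficient would discard it. This is a reason to report both.
- **The stakes are low.** A reader might infer that the dose rationale rests on this coefficient. It does not: Protocol 1.4 relies on earlier studies and modelling, and Protocol 7.3 says thrombin generation will not guide dosing or conduct.

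**Conclusion.** The point holds as a gap in the method with a known consequence. SAP 2.4.6.1.3 builds a correlation on about nine repeated pairs per patient and does not account for the repetition. Followed literally, it yields a number that in general equals neither the within- nor the between-patient association.

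The size depends on assumed values. Across the settings shown, a within-patient correlation of −0.60 appears as anything from −0.57 to −0.30, and one of −0.20 as −0.50 or −0.68. The direction of the error cannot be stated from the documents. If ICCs are very small, or the two associations and the two ICCs agree, the blend does little or no harm. Inflated error rates arise only if a naive interval or test is added.

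This is a low-priority improvement. No primary, secondary or dosing conclusion depends on it.

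**What to change.** Amend SAP 2.4.6.1.3 to:

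- Report a within-patient (repeated-measures) correlation on patient-centred pairs, or a mixed model of log peak thrombin on AT with a random patient intercept. In the model, enter AT as the patient's mean plus the deviation from it, so that the slope on the deviation is purely within-patient.
- Report the between-patient correlation of patient means beside it.
- State which visits enter, with or without Day 1 and screening, and give the number of patients and pairs left after the 48-hour exclusion.
- Use patient-clustered intervals, such as a bootstrap that resamples patients, if any interval is shown.

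The cost is a few lines of extra code and two coefficients to report instead of one. It needs no new data or visits.
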